Understanding Social Situations (USS): Training to improve social function in people with psychosis

NCT04557124

November 1, 2023

PROJECT DESCRIPTION

1. Principal Investigator: [name].

Project Title: Understanding Social Situations (USS): Training to improve social function in people with psychosis

2. Purpose: We propose to evaluate the efficacy of Understanding Social Situations (USS), a behavioral training targeting social cognitive skills. The current proposal is to conduct a fully powered, rigorous randomized controlled trial to test the efficacy of USS versus an active control condition. One hundred twenty Veterans with psychotic spectrum disorders (PSD) will be randomized to 2 months of USS or an active control (AC) intervention matched for duration, therapist contact, and mode of delivery. Key social functioning outcomes will be measured using a multi-method approach of self-report, role-play, and experience sampling, conducted pre-intervention, post-intervention, and at 2 month follow-up, with an additional limited assessment at treatment mid-point.

Primary Aim:

Aim 1: Examine the efficacy of USS in improving social functioning.

H1.1: Compared to AC, USS will be associated with greater improvements on the Social Functioning Scale.

Secondary Aims:

Aim 2: Examine the efficacy of USS in changing real-world social behaviors.

H.2.1: Compared to AC, USS will be associated with greater improvements in real-world social behaviors, as measured by ecological momentary assessment (EMA).

Aim 3: Examine efficacy of USS in improving social interaction skills.

H.3.1: Compared to AC, USS will be associated with greater improvements on the UCSD Social Skills Performance Assessment, a performance-based measure of social skills.

Aim 4: Examine durability of USS effects on clinician and self-rated social functioning, real-world social behaviors, and social skills.

H 4.1 Above group differences will be maintained at 2-month follow-up.

Exploratory Aims: Examine mechanisms of USS effects.

- A. Target engagement and validation: examine impact of USS on a measure of USS content learning (USS Skills Test) and relationship between content learning and improvement in social functioning.
- B. Personalization: explore baseline cognitive, treatment dose, symptom clusters and demographic variables as potential moderators of USS efficacy.

Additional Aims: collect normative (psychiatric control) information about social function in non-psychotic psychiatric sample in order to better characterize the nature of social function and factors impacting social interactions in Veterans with versus without psychosis.

3. Background:

Functional disability is a core, defining feature of psychotic spectrum disorders (PSD), and persists even when psychotic symptoms are in remission⁴. A majority of people with schizophrenia are not competitively employed, have never been married, have some difficulty with self-care, and have poor community integration⁵⁻⁸. Impairments in social function are also prominent, leading to significant social isolation and impeding recovery⁹. Social function deficits are present prior to illness onset¹⁰, persist throughout different phases of the illness¹¹, and are more severe in PSD than in other serious mental illnesses¹². Pharmacotherapy and other existing treatments fall short of significantly improving social and community functioning, and social re-

integration is among the top treatment needs both consumers and clinicians feel are not adequately addressed by existing interventions^{13, 14}.

Poor social function in people with psychotic spectrum disorders (PSD) has been linked to significant impairments in social cognition, or how a person processes, interprets and responds to uniquely social information, including complex inferences a person makes about other people's thoughts, feelings and actions. In an effort to improve social functioning, a number of interventions targeting complex social cognitive skills have been developed in recent years. These treatments show some promise, but many of the trials have had significant methodological weaknesses, there is limited data about effects on everyday social functioning outcomes, and nearly all of the work has been conducted in non-Veteran samples. The only group that did examine social cognitive training in Veterans did not find effects on social functioning. Needed now are additional rigorous social cognitive treatment efficacy trials, specifically in Veteran samples, and with an emphasis on everyday social functioning outcomes.

[figure not shown]
Impairments in concentration, memory, and problem solving are also common in PSD and can make it challenging to learn complex social cognitive skills. With this in mind, we developed a social cognitive training that leverages successful methods from bottom-up cognitive remediation to reduce cognitive load and aid with acquisition of social cognitive skills. The training was developed under an NIMH R34 grant and is called Understanding Social Situations (USS). To date, we have developed and refined USS training content, created a treatment manual, conducted a single-arm pilot of the intervention, and collected preliminary data on the effects of USS when incorporated into a psychosocial rehabilitation program. The current proposal is to conduct a fully powered, rigorous randomized controlled trial to test the efficacy of USS versus an active control condition.

4. Significance:

Schizophrenia and other psychotic disorders are among the top 10 causes of disability in the world², with an economic burden of over \$150 billion³. Psychotic disorders are characterized by significant functional disability, including severe impairments in social and community function. Existing treatments fall short of significantly improving social and community functioning, and social re-integration is among the top treatment needs consumers feel are not adequately addressed by existing interventions. If effective, the proposed intervention has the potential to promote rehabilitation and recovery efforts by meaningfully impacting the social lives and wellbeing of Veterans with psychosis.

5. Research Plan:

Overview: We propose a randomized, controlled trial investigating the efficacy of Understanding Social Situations (USS) in improving social functioning in participants with psychotic disorders. We will examine the efficacy of USS on social functioning (primary outcome), real-world social interactions, and social skills. We will also explore moderators and mediators of treatment effects, specifically the impact of baseline variables on treatment

efficacy and the relationship between USS content knowledge test and social functioning change. One hundred twenty participants will be randomized to two months of individually administered USS or a matched active control training. Comprehensive assessments will occur at baseline, end of training phase, and two-month follow-up, with an additional assessment of the primary outcome and of USS content-related skill (treatment target) at training mid-point. We will additionally obtain baseline-only social function information for a normative (non-psychotic) psychiatric sample, in order to better understand and characterize the patterns of social interactions in our primary psychotic spectrum sample.

Participants:

Psychosis sample: Participants will be Veterans with a psychotic spectrum diagnosis (PSD). Specific inclusion/exclusion criteria will be as follows: diagnosis of psychotic disorder (e.g. schizophrenia, schizoaffective disorder, delusional disorder, psychosis NOS); no prior exposure to USS training, age 18 and

over; not meeting criteria for substance use disorder in past 30 days; psychiatric stability as evidenced by minimum of 30 days since last psychiatric hospitalization and since last change in psychiatric medications; no evidence of developmental disability in chart or on baseline assessment; no severe, uncorrected auditory/visual impairment; no diagnosis of medical or neurological illness known to impair brain function including dementia, presence of seizures, history of head trauma with loss of consciousness > 1hr, or clear cognitive sequelae from other illness or injury, per medical chart review; fluency in English; ability to provide legal written informed consent (i.e. the participant does not have a conservator); not currently enrolled in another treatment study targeting, or expected to impact, functioning. We hope to randomize approximately 120 Veterans into the study conditions.

Psychiatric control sample: Specific Inclusion/exclusion criteria for the psychiatric control group: age 18 and over; currently receiving mental health treatment; no lifetime diagnosis of psychotic disorder (e.g. schizophrenia, schizoaffective disorder, delusional disorder, psychosis NOS) based on clinical interview; not meeting criteria for PTSD in the past 30 days based on clinical interview; not meeting criteria for substance use disorder in past 30 days based on clinical interview; not meeting criteria for a major depressive or manic episode in the last 30 days based on clinical interview; psychiatric stability as evidenced by minimum of 30 days since last psychiatric hospitalization, no current high risk for suicide flag on their chart, and no active suicidal or homicidal ideation in that past 30 days; no evidence of developmental disability in chart or on baseline assessment; no severe, uncorrected auditory/visual impairment; no diagnosis of medical or neurological illness known to impair brain function including dementia, presence of seizures, history of head trauma with loss of consciousness > 1hr, or clear cognitive sequelae from other illness or injury, per medical chart review; fluency in English; access to a smartphone to which they are willing to receive surveys via text message; ability to provide legal written informed consent (i.e. the participant does not have a conservator); We hope to have approximately 20 participants complete study procedures.

Measures for primary psychotic-spectrum sample:

Baseline assessments will consist of demographic, intelligence, psychiatric, cognitive, social function and knowledge of USS training content measures. Post-training and 2-month follow-up assessments will mirror baseline assessments, with the exception of diagnostic interviews and IQ estimate, which will only be administered at baseline. An additional assessment of the primary outcome, SFS, and of the proposed mediator of treatment effects, USS Skills Test, will occur at treatment mid-point. Please refer to Assessment Timeline below. The baseline assessment will be split into a screening assessment to confirm study eligibility (demographics, WASI, SCID, SFS), and a subsequent baseline assessment for those who pass the screening (PANSS, PHQ-9, QLS, MCCB, SSPA, USS Skills Test)

Intelligence: The Wechsler Abbreviated Scale of Intelligence (WASI⁶⁸, 2-subtest estimate) will be used to obtain estimates of current intelligence (IQ Estimate score). The WASI 2-subtest IQ estimate correlates highly ($r=.87$) with the Wechsler Adult Intelligence Test⁶⁹, the most commonly used and accepted measure of intellectual function. It also has high internal consistency reliability ($r=.93$ for adult sample), and 2-12 week test-retest stability ($r=.85$). The WASI will be used to characterize the study sample and screen for intellectual disability (IQ < 70) at baseline.

Diagnostic and Symptom: The Structured Clinical Interview for DSM-V (SCID⁷⁰) will be used to confirm psychotic spectrum diagnoses. The SCID is the most commonly used semi-structured interview for obtaining DSM-V diagnoses. Modules A through E will be used to determine presence of psychotic and mood syndromes, substance use history, and differential diagnosis. The Positive and Negative Syndrome Scale (PANSS⁷¹) will be used to characterize participants by assessing the presence and severity of psychiatric symptoms. The PANSS is an interviewer-rated scale indexing the core symptoms of psychosis as well as a broad range of general psychiatric symptoms *including depression and anxiety*. Each symptom is rated on a Likert-type scale ranging from 1-7, for total score range of 30 to 120. Initial reports using this scale provide evidence of good internal reliability for the three subscales ($\alpha = .73$ to $.83$), with adequate test-retest reliability over 3-6 month inpatient phase ($r=.60$ to $.80$) and good interrater reliability ($r=.83$ to $.87$). Within our research group, ICC's against gold standard, study PI, range from $.85$ -.97 for PANSS components. For initial exploratory analyses of symptom severity as a potential moderator of treatment effects, PANSS Total Score will be used. As warranted, subsequent analyses may examine the Positive, Negative, and General symptom

subscales, as well as Depression and Anxiety scores. The Patient Health Questionnaire (PHQ-9) will also be used to assess depression. The PHQ-9 is a commonly used, 9-item, likert-style, self-report measure (Kroenke, Spitzer & Wiiliams, 2001). The Quality of Life Scale (QLS⁹⁵) will be used to assess interviewer-rated functioning. In addition to providing a total score, this well known measure of functioning can be subdivided into four separate domains; intrapsychic foundations, interpersonal relations, instrumental role functioning, and common objects and activities.

Assessments			Pre	Mid	Post	FU
Timeline	Duration	Measure type				
Demographics/Psychosocial	10 min	sample characteristics, potential moderators	X			
Wechsler Abbreviated Scale of Intelligence (WASI, 2 subtest)	20 min	IQ estimate, sample characteristics, potential moderator	X			
Structured Clinical Interview for DSM (SCID)	60 min	diagnostic, sample characteristics	X			
Quality of Life Scale (QLS)	30 min	social functioning, sample characteristics, potential moderator	X		X	X
Positive and Negative Syndrome Scale (PANSS)	30 min	symptom severity, sample characteristics, potential moderator	X		X	X
Patient Health Questionnaire-9	2 min	Depression symptoms	X		X	X
Matrics Consensus Cognitive Battery (MCCB)	60 min	cognition, sample characteristics, potential moderator	X		X	X
Social Functioning Scale (SFS)	15 min	social function primary outcome, potential moderator	X	X	X	X
7-day EMA assessment	3min/each assessment (total 12 min/day)	social function secondary outcome	X		X	X
Social Skills Performance Assessment (SSPA)	10 min	social function secondary outcome	X		X	X
USS Skills Test	5 min	social cognition training target, potential moderator	X	X	X	X

Cognitive: Cognition will be assessed using the MATRICS Consensus Cognitive Battery (MCCB⁷²). The MCCB was developed by an expert panel of researchers, under NIMH contract, as a broad yet sensitive measure to assess cognitive change in treatment studies. The MCCB includes assessment of 7 domains: speed of processing, attention/vigilance, working memory, verbal learning, visual learning, reasoning and problem solving, and social cognition. While an overall composite score is available, in recognition of differences between neurocognitive and social cognitive impairments, it is becoming more and more common in studies of neurocognitive function in psychosis to calculate a 6-domain composite score, omitting the social cognitive domain. This composite score will be used for initial exploratory analyses of cognition as a potential moderator of treatment effects.

Social Functioning primary outcome: Social functioning will be measured using the interviewer-administered Social Functioning Scale (SFS⁷³), which assesses social functioning across seven domains: social engagement/withdrawal, interpersonal behavior/communication, prosocial activities, recreation, independence—competence, independence—performance, and employment/occupation. The SFS is one of the best known measures of social functioning in schizophrenia, and was one of two social function measures nominated by experts and selected by a RAND panel for a large-scale investigation of measures to assess real-world outcomes⁷⁴ based on its psychometric properties, sensitivity to change, relationship to symptoms, Version 11/01/2023

and comprehensiveness. Importantly, our pilot data indicates that the SFS is sensitive to the effects of the USS intervention. Total score will be used as our primary outcome.

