COVID-19 Pandemic Procedures: As long as COVID-19 remains a significant concern, this study will conduct the majority of research procedures remotely, via VA-approved telehealth platforms, for all participants recruited during the pandemic. Conducting as many procedures remotely as possible will help to reduce the length of time that in-person interactions are taking place and thus increase staff and participant safety during this pandemic.

Remote procedures: In the setting of the novel coronavirus pandemic, the consent form will be mailed to subjects after participating in a phone screening to determine initial eligibility. Upon receipt of the consent form, the consent form will be reviewed with the subject during a telehealth visit, signed and returned to the research team when the participant comes in for their in-person visit. The majority of the study assessments will be conducted using VA-approved video conference platform. Appointments conducted via video will not be recorded, with the exception of the USS/active control sessions, which are also recorded during in-person sessions, to allow for fidelity ratings to be conducted later.

Any virtual sessions will follow safety guidelines that are used in routine VA telehealth care, including the following:

1. Communicating to the participant the importance of having private space to ensure their confidentiality during study sessions
2. Determining an emergency contact, and the location/address of participant at the time of the study session
3. Using available elements of the video platform to ensure confidentiality (e.g., “locking” the virtual meeting room)

When administering assessments that measure depression or SI (PANSS, PHQ-9, or SCID) remotely, in addition to the safety precautions above, we will ensure that the PI is readily available. If the subject expresses SI, whoever is doing the assessment will contact the PI who will do a more detailed imminent risk assessment over the phone. If the PI believes there is risk and is concerned for the study participant's safety, 911 will be called for a welfare check.

In order to allow for remote administration and to limit in-person visits, some changes to the MCCB cognitive assessments have been made including:

- Eliminating spatial span, BVMT and mazes subtests
- Replacing the MCCB Symbol Coding with an oral version of the Symbol Digit Modalities Test,
- Using the oral version of Trails A and B instead of the standard version of the Trails A

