In-person study visits conducted at baseline, post-training and follow-up time points will kept as brief as possible, and include the following safety guidelines:

- For any in-person visits that take place, one day prior to the visit and/or at time of visit, participants will be asked the standard COVID-10 screening questions in place at VACHS, and be asked to use a hand sanitizer upon entering the office.
- Participants will be required to wear a 2-ply face mask when in the room with research staff, and if they do not have one, one will be provided for them.
- Staff will utilize masks, gloves, face shields and social distancing during study visits, and will sanitize the office between each in-person visit and at the end of the day.

Recruitment: Veterans with and without psychotic spectrum diagnoses will be recruited from VACHS outpatient clinics via flyers, presentations of study to treatment teams, other research groups, and MH clinicians. The study will also be presented to Veterans during community meetings of the VACHS Psychosocial Rehabilitation and Recovery Center, which serves Veterans with serious mental illness. Recruitment will also

occur through our re-contact repository (those who have participated in our group's prior studies and agreed to be re-contacted with information about additional research opportunities), with the exception of those who participated in the initial USS treatment development trial. We may also pull MH clinic appointment lists, screen upcoming appointments for potential eligibility, alert providers to upcoming appointments with potentially eligible participants, and ask that they refer those who are interested in learning more about the study. We will also offer a small incentive to past/current participants who refer other eligible Veterans. For Veterans with psychotic spectrum diagnoses only, we may also send out study solicitation letters (with opt-out cards), as has previously been approved by the HSS.

Randomization for psychotic spectrum sample: Veterans who meet eligibility criteria and consent to study participation will be randomized to receive either USS or AC in a 1:1 ratio. Randomization will be stratified by baseline SFS score, using a permuted block design with variable block size. The randomization scheme will be computer-generated by the statistician and the allocation sequence will be concealed.

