Analysis of Real World Social Behaviors (Aim 2): Ecological momentary assessment (EMA) analyses will be conducted using a multilevel modeling approach⁸⁷. Analyses handle data estimation with a restricted maximum likelihood approach. Data will be organized hierarchically, with within-person/random EMA prompts across the study period nested within people. Random (within-person) coefficients will be estimated for each person at Level 1, while fixed (between-person) coefficients will be estimated at Level 2. Within-person variables will be centered at Level-1 and between-person variables will be grand mean centered at Level-2⁸⁸⁻⁹⁰. We will examine associations between [e.g., attributions] and [e.g., number of interactions] at Level 1, and fit models with fixed [e.g. group, age, gender] main effects at Level 2. We will also examine [L1] and [L2] cross-level interactions.

Analysis of Social Interaction Skills (Aim 3) and Durability (Aim 4): The secondary outcome social interaction skills, assessed by SSPA, will be compared between USS and control using a repeated measures linear mixed model similar to that described in the analysis of the primary outcome. Durability will also be compared between USS and control using the mixed model. For primary and secondary outcomes, linear contrasts will be used to estimate intervention group differences and 95% confidence intervals at the 2-month FU assessment.

Analysis of Mediation (Exploratory Aim A): We will explore content learning (USS Skills Test) as a potential mediator of the relation between intervention and changes in social functioning. Direct and indirect effects will be estimated using a structural equation model. Mediation (i.e. indirect effects) will be tested using the bootstrapping approach⁹¹.

Analysis of Moderation (Exploratory Aim B): Heterogeneity of treatment effects (HTE) for the primary outcomes will be explored in subgroups of participants based on baseline characteristics including cognition, symptom clusters, illness characteristics, medication dose (chlorpromazine equivalents) and demographic variables. These subgroup analyses are aimed at determining whether there is differential effectiveness of the interventions among participant subgroups. Evidence of HTE will be based on tests of interaction within the longitudinal model structure described above.

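### Does the shortened cognitive battery leave the exploratory cognition moderator without a usable definition?

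*Combined protocol and SAP*

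**What the plan says.** The measures section (Cognitive) chooses the MCCB, which covers seven domains. It notes that investigators increasingly "calculate a 6-domain composite score, omitting the social cognitive domain", and then commits to that score: "This composite score will be used for initial exploratory analyses of cognition as a potential moderator of treatment effects".

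The COVID-19 Pandemic Procedures section states that, to permit remote testing and limit visits, "some changes to the MCCB cognitive assessments have been made including" the items that follow. Three tests go altogether: "Eliminating spatial span, BVMT and mazes subtests". Two more give way to spoken forms. Symbol Coding is exchanged for an oral Symbol Digit test, and for trail-making the plan describes "Using the oral version of Trails A and B instead of the standard version of the Trails A".

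The same section retains "In-person study visits conducted at baseline, post-training and follow-up time points", to be kept short. It ties remote working to recruitment during the pandemic and gives no end date.

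Analysis of Moderation (Exploratory Aim B) lists "baseline characteristics including cognition, symptom clusters, illness characteristics, medication dose (chlorpromazine equivalents) and demographic variables" and tests each by an interaction term in the longitudinal model. It does not say which cognition score is meant. The assessments timeline still shows the MCCB as a 60-minute battery at pre, post and follow-up, with no variant.

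**The concern.** The plan names one cognition score in advance, which normally stops an analyst from picking the version that gives the most interesting interaction. A later section changes the inputs to that score and supplies no scoring rule. On a plain reading, the named composite and the battery actually given no longer match.

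Two situations are possible. If everyone had the modified battery, the composite has to be rebuilt from what is left. If some had the full battery and some the modified one, two versions have to be put on one scale, and version would follow recruitment period. In either case the moderator's definition is settled outside the plan. The word introducing the list of changes also leaves open whether the list is complete.

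At stake is the reading of one moderator that matters to the rationale of Understanding Social Situations (USS), since the training was designed to work around cognitive impairment.

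**Working it through.** The plan gives no figure for this point, so the check compares sections and follows the score to each place where it could be used.

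1. **Count of changes.** Subtests removed: 3. Subtests replaced: 2 (Symbol Coding; standard Trails A). Altered: 3 + 2 = 5. Domains in the named composite: 7 − 1 = 6. The mismatch between the two sections is confirmed.

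2. **Search for a scoring rule.** The Cognitive paragraph, the assessments timeline, the COVID-19 section, General Approach, Analysis of Moderation and Plan for Missing Data give no rule for prorating, norming or bridging. The appendices are cited for the EMA protocol and the control manual, not for MCCB scoring. The gap is confirmed.

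3. **Can the composite still be formed?** That depends on which subtests feed which domain and on what the test's scoring rules allow when a subtest is absent. The document gives neither and only cites the manual. It therefore cannot be shown from the document that the composite is impossible to compute, or that any domain loses all its tests. What can be shown is that the construction is unstated.

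4. **Is a sensible construction blocked?** No. The ban on imputation in General Approach applies to primary and secondary analyses, so it does not forbid a prorated composite in an exploratory one. An analyst could prorate over the remaining tests, standardise within battery version, or average the tests common to all participants.

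5. **Where does the score enter?**
   - *Sample size.* Inputs are a 9-point SFS difference, SD 13.1, two-sided 0.05, 90% power and 1:1 allocation. The normal approximation gives 2 × (1.960 + 1.282)² × (13.1/9)² ≈ 44.5, so 45 per group. The t-test version gives 45.5, so 46, which is the plan's figure. No cognitive input is used.
   - *Primary analysis.* The model has intervention, time, their interaction and baseline SFS. Cognition could enter only as an added baseline covariate, if it were found to predict dropout.
   - *Secondary outcomes.* These are EMA and the role-play skills test. Cognition is not an outcome under any aim.
   - *Exploratory Aim B and sample description.* The score is used here.

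6. **Could the choice of rule favour an arm?** The baseline assessment precedes randomisation, so the score cannot be affected by treatment. Battery version depends on when a person was recruited, not on arm, and permuted blocks keep the arms close to balanced over time. A rule applied without regard to arm changes what is measured and how noisily, but does not tilt the comparison.

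7. **Can the effect on precision be sized?** Not from the document. A loss of sample size would arise only if participants given the modified battery were excluded, which the plan nowhere proposes, and the share on each version is not stated (0 to 120 of 120). If all had the same modified battery, no one is lost. If versions are pooled, nothing in the document allows an estimate.

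**The case for a change.** The strongest case for amending runs as follows. Cognition is the first moderator named in Exploratory Aim B and is central to why USS was designed as it was. The authors took the trouble to pre-specify the score, and the pandemic changes removed that protection without replacing it. If both versions were used, version follows recruitment period and randomisation is stratified only by baseline SFS, so a pooled score would carry some calendar effect. A short paragraph would settle it: for example, a mean of baseline z-scores over the unchanged non-social subtests, calculated alike for everyone.

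Part of this stands. The rule is missing, and if two versions exist an analyst should look at version in the moderator model. Two things weaken the case for a mandated change.

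First, the pre-specification was light. The composite is assigned to initial exploratory work, and the PANSS is handled the same way, with the total score first and subscales later if warranted. Other cognition scores were always open, and the WASI IQ estimate, listed in the timeline as a potential moderator, is not among the altered tests.

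Second, the suggested replacement is a trade-off. An unweighted mean of subtests gives more weight to any domain with more surviving tests, unlike a domain-based composite. It leaves the trial's own oral substitutes out of the main score, narrows the construct, and relies on retained subtests that the document does not name. A careful statistician could reasonably choose differently.

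**Conclusion.** No change to the plan follows. The sections do not match and the scoring rule is absent, but this is missing detail for one exploratory moderator, of a kind that analysts fill routinely and report when they present the result: which subtests were used, how the oral substitutes were scaled, how many participants had each version and how version was handled.

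The consequence is confined to Exploratory Aim B and the cognitive description of the sample. Five subtests are altered and the number of participants affected is unknown. No defensible figure can be put on the change in the interaction estimate.

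This rests on three conditions: the cognition score stays exploratory and supports no confirmatory claim; whatever rule is used is applied alike in both arms; and the baseline battery is given before randomisation, as the procedures state. If cognition were promoted to a confirmatory moderator, the score would need a written definition first.
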